to contribute to the control of this pathology. . Therefore, combining medications with different mechanisms of action, in low doses, could be a useful strategy not only to prevent DM2, but also to prevent macro and microvascular complications early.

PROBLEM STATEMENT

¿What is the effect of low-dose combination of linagliptin + metformin compared to metformin alone on pancreatic beta cell function, insulin resistance and cardiovascular function in patients with prediabetes and overweight/obesity?

HYPOTHESIS

Of Work

The low-dose combination of linagliptin + metformin has a greater effect on pancreatic beta cell function, insulin resistance and cardiovascular function compared to metformin alone in patients with prediabetes and overweight/ Obesity.

Null

The low-dose combination of linagliptin + metformin has no greater effect on pancreatic beta cell function, insulin resistance and cardiovascular function compared to metformin alone in patients with prediabetes and overweight/ Obesity.

OBJETIVES

General: Evaluate the effect of low-dose combination of linagliptin + metformin against metformin alone on pancreatic beta cell as function, insulin resistance and cardiovascular function in patients with prediabetes and overweight or overweight or Obesity.

Specific

- Evaluate insulin resistance, pancreatic beta cell function and cardiovascular function in a group of patients with prediabetes, treated with Metformin 1700 mg/day for 6 months, at the start of surgery and at 6 months.
- Evaluate insulin resistance, pancreatic beta cell function, and cardiovascular function in a group of patients with prediabetes treated with the combination of linagliptin 2.5mg every 24 h + metformin 1700 mg every 24 h for 6 months, at the start of intervention and at 6 months.
- Compare markers of cardiovascular risk before and after treatments in the 2 study groups.
- Compare insulin resistance and pancreatic beta cell function between study groups at the end of the intervention.
- Know glucose metabolism by oral glucose tolerance curve at baseline and end of treatment in the study groups.
- Determine changes in body composition.

Secondary objectives

- Evaluate therapeutic adherence in study groups.
- Know the incidence of type 2 diabetes mellitus in each study group during follow-up to this project.
- Know renal function by depuration of creatinine and albuminuria at the beginning and end of the study in the study groups.

STUDY DESIGN.

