Patients with CTOG glucose intolerance are those who will be invited to participate in the trial and those who accept will continue with a more thorough metabolic evaluation. For this purpose, patients will have completed a medical history and the following studies:

1) Fasting basal blood samples for measurement of:

- Blood count
- Lipid profile
- Insulin for homa-IR determination, HOMA-B, insulin sensitivity, insulin secretion and pancreatic beta cell function.

2) Determination of body composition (% visceral fat, % total body water, bone mineral density, etc.) using DEXA analysis. Here the patient scrutiny ends and if at this time the patient agrees to participate in the phase of intervention, the following will be carried out, after explanation and signature of informed consent letter.

- 1) Cardiovascular function assessment: This will be done through standard echocardiography area of the High Specialty Regional Hospital.
- 2) Evaluation of renal function: Through 24-hour urine collection, which will measure creatinine clearance and 24-hour albuminuria.
- 3) Randomization: It will be done by using a table of random numbers generated by a computer program. Patients will be randomized to receive, for 6 months, one of the following 2 interventions: 1) Dosis of *linagliptin 2.5 mg* every 24 h + *metformin 1700 mg* every 24 h y 2) 1 tablet every 12 h of Metformin 850mg.

THIRD PHASE: *Intervention and follow-up*

All patients will receive nutritional guidance and physical activation during the study. Once patients have all baseline measurements and have met the selection criteria, they will be randomized to one of the two interventions. All patients will have monthly follow-up and global clinical evaluation and treatment attachment, and anthropometry.

FOURTH PHASE: *Ending of the study (final measurements)*.

At 6 months of treatment, patients will be quoted again in fasting, on two different occasions,

- 1) FIRST APPOINTMENT: For measurement of glucose and fasting insulin, determination of body composition by imdoanciometry and performance of CTOG.
- 2) SECOND APPOINTMENT: Evaluation of cardiovascular function by echocardiography, and renal function by depurating creatiline and albumin in urine of 24h.

STATISTIC ANALYSIS

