The data will be presented with descriptive statistics, mean and standard or median deviation and interquartile travel, as well as percentages and incidence. For comparisons of numeric variables between study groups, we will use Student t if the distribution of the data follows a normality pattern, otherwise the Mann-whitney U test will be used; to compare qualitative variables we'll use square Chi. Analysis by intent to be treated and analyzed by protocol shall be performed and considered as significant when the p-value is <0.05. For the analysis and presentation of the data we will use the sPSS Version 15 and GraphPad Prism program 5.

ETHICAL ASPECTS

Ethical standards, Regulations of the General Health Law on Health Research and the Helsinki Declaration of the World Medical Association of the 64th General Assembly, StrongHold, Brazil in 2013 and current international codes and standards of good clinical research practices. Special attention will be given to taking care of the privacy and

autonomy of the patient. Once the patient has been informed about the study and agrees to participate in it, and since it involves a greater risk to a minimum, the signature of informed consent letter will be requested.

BIBLIOGRAPHIC REFERENCES:

4. Villalpando S, de la Cruz V, Rojas R, Shamah-Levy T, Avila MA, Gaona B, et al. Prevalence and distribution of type 2 diabetes mellitus in Mexican adult population: a probabilistic survey. *Salud Publica Mex* [Internet]. 2010 [cited 2018 Apr 7];52 Suppl 1:S19-26. Available from: <http://www.ncbi.nlm.nih.gov/pubmed/20585724>

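### Body composition is measured by DEXA at baseline but by an illegible term at 6 months; if these are two methods, the planned before-after change cannot be interpreted

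*Combined protocol and SAP*

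**What the plan says.** **Baseline (Methods, Recruitment of patients, metabolic evaluation):** "Determination of body composition (% visceral fat, % total body water, bone mineral density, etc.) using DEXA analysis".

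**6 months (Fourth phase, first appointment):** "determination of body composition by imdoanciometry and performance of CTOG".

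**Objective (Objectives, Specific):** "Determine changes in body composition". No between-group contrast is attached to it. For other outcomes there is one: "Compare insulin resistance and pancreatic beta cell function between study groups at the end of the intervention".

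**Analysis (Statistic analysis):** "The data will be presented with descriptive statistics, mean and standard or median deviation and interquartile travel". For testing: "For comparisons of numeric variables between study groups, we will use Student t", with Mann-Whitney as the non-normal alternative and chi-square for qualitative variables. No within-group test is planned, and no conversion or calibration between measurement methods is described.

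**Variables section:** the four dependent variables are glucose homeostasis, insulin sensitivity, beta cell function and cardiovascular function. Body composition is not among them and has no row in the variables table.

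**The concern.** The objective asks for change, so each patient's 6-month value has to be set against the baseline value. That works only if both come from the same method. As written, the method is clear at baseline and illegible at 6 months, and the illegible word does not resemble the acronym used earlier. Someone following the plan could not tell which measurement to perform. If a second method is used, a reported change in body composition, the quantity the objective names, would have no clear meaning. Once a patient's 6-month value has been taken by the other method alone, the like-method pair for that visit cannot be recovered.

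**Working it through.** The plan states no figure for this outcome, so there is none to reproduce. The check compares the text at the two visits and then traces what a method difference would do to each possible analysis.

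**1. Is the same procedure named at both visits?**

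| Assessment | Baseline or screening | 6 months | Same? |
|---|---|---|---|
| Oral glucose tolerance | CTOG | CTOG | yes |
| Cardiovascular function | echocardiography | echocardiography | yes |
| Renal function | 24-hour urine, creatinine and albumin | 24-hour urine, creatinine and albumin | yes |
| Body composition | DEXA | *imdoanciometry* | cannot be confirmed |

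Only body composition changes term. The document does not define the 6-month word, use it at baseline, or mention DEXA at 6 months.

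**2. Effect on before-after change.** Let T0 and T6 be the true values. Suppose DEXA reads T, and a second method reads a + bT, apart from error. Then

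observed change = a + b·T6 − T0 = (T6 − T0) + [a + (b − 1)·T6].

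The bracket is the between-method difference. It vanishes only if a = 0 and b = 1. The documents give neither a nor b, so its size is unknown.

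**3. Effect on the between-arm comparison.** Write T6 = T0 + δ. Observed change is then a + (b − 1)·T0 + b·δ, and the arm difference is

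b·(mean δ in arm A − mean δ in arm B) + (b − 1)·(mean T0 in arm A − mean T0 in arm B).

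- The constant a cancels.
- The second term has expectation zero under randomisation, but it adds noise if b ≠ 1.
- The treatment effect is multiplied by b, so it is on the second method's scale.
- With no treatment effect the arms are exchangeable, because both use the same method at each visit. The type I error is therefore kept whether or not the offset is constant.

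Simulation agrees (14 per arm, 40,000 trials). With a constant offset of 0, 0.25, 0.5 or 1.0 SD of change, the between-arm Student t rejected in 5.0%, 5.0%, 5.0% and 4.9% of trials. With an assumed proportional plus additive difference it rejected in 5.0% on change scores and 5.1% on 6-month values.

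**4. Precision.** A comparison of 6-month values uses one method only, so mixing methods costs it nothing. For change scores with equal SDs, the ratio of standard errors (two methods to one) is √[(1 − r_two)/(1 − r_one)], where r is the correlation between baseline and 6-month values. The ratio is 1 if the correlations are equal and above 1 if r_two is lower. The documents give neither correlation.

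**5. Illustration only, for an analysis the plan does not contain.** With the protocol's stated 14 evaluable patients per group, the 95% interval for a within-group mean change has half-width t(0.975, 13)/√14 = 2.160/3.742 = 0.577 SD of change. With no true change, assumed offsets of 0.25, 0.5 and 1.0 SD would make that interval exclude zero in 14%, 41% and 93% of trials, against 5% with no offset (noncentral t). These figures hold for any offset in any variable at this n. They are not evidence about the two methods here.

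**The case against.** **The mismatch rests on one unreadable word.** The translation is poor elsewhere. The first specific objective has patients assessed "at the start of surgery and at 6 months" in a trial without surgery, while the parallel objective for the other arm refers to the start of the intervention. The 6-month word could be a slip for DEXA. The visit lists could also be incomplete, with both methods used at both visits. This stands: a second method is not established, and impedance is an inference. What remains is that the plan does not legibly state the 6-month method, while every other repeated assessment is recognisable at both visits.

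**No planned test is harmed.** The analysis section tests between groups only, and step 3 shows those tests stay valid. This also stands. Within-group change would not isolate the drug effect even with one method, because "All patients will receive nutritional guidance and physical activation during the study". The objective still asks for change, and descriptive statistics on change would be reported.

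**The illustration in step 5 depends on assumed offsets and on the stated n.** Agreed. It carries no weight in the conclusion.

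**A stronger reading is tempting:** that the trial switches from DEXA to impedance and that its treatment comparison is therefore biased. The documents support neither half. The switch is not legible in the text, and a method difference shared by both arms does not create a false treatment effect.

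**Conclusion.** The point holds conditionally and is minor. The 6-month body-composition method is not legibly specified and does not read as the baseline method, although a specific objective is to determine change. If the methods differ, descriptive within-patient and within-group change cannot be interpreted, and a between-arm comparison of change scores could lose precision and be reported on a mixed scale. If the term was meant as DEXA, only the wording is at fault.

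No size of bias can be given, because the documents contain no between-method offset, scale factor or correlation. The conclusion that type I error is preserved rests on randomisation and on both arms using the same method at each visit. The four dependent variables, and so the main hypothesis, are unaffected.

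**What to change.** Correct the 6-month term. State the same body-composition method, device and list of parameters for both visits, before any further 6-month measurements are taken. Add that change will be computed only from values obtained by the same method. The documents do not say whether enrolment has begun. If it has, DEXA at 6 months remains possible for every patient with a DEXA baseline who has not yet reached that visit.

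Cost, by case:

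- **The term means DEXA:** a wording correction only.
- **DEXA at both visits:** one scan per patient at the existing 6-month appointment in place of the other method, that is 2 × 14 = 28 to 2 × 17 = 34 scans on the protocol's stated group sizes. No unit costs are given.
- **Impedance at both visits, replacing DEXA at baseline:** no extra visit, but the bone mineral density listed at baseline is lost.

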Type of Study: Clinical trial (randomized, controlled and triple-blind).

MATERIAL AND METHODS.

Study universe: Mexican patients with prediabetes and overweight/obesity.

Study population: Mexican patients with prediabetes and overweight/obesity, from the State of Guanajuato.

Place of realization: Hospital Metabolism Laboratory of Division of Health Sciences of the University of Guanajuato, León, Gto.

Type of sampling: Non-probabilistic, of consecutive cases.

Sample size: The calculation of the sample size was based on the formula for comparing proportions. We hope that the low-dose combination of linagliptin + metformin will improve the outcome variables (insulin resistance, pancreatic beta cell function and cardiovascular function) by at least 75%, metformin use alone achieves this only by 30%(44.46), so the study is designed to detect a minimum difference of 45% between study groups with a type I (alpha) error of 0.05 and a sample power of 80% , and according to the following formula(70):

$$n = \frac{(Z\alpha/2 + Z\beta)^2 p^- (1-p^-)(r + 1)}{(d)^2 r}$$

Where,

$$(Z\alpha/2 + Z\beta)^2 = 7.9$$

p^1 = proportion of individuals in the best treatment who failed to achieve improvement = 0.25

p^2 = proportion of individuals in the worst treatment who failed to achieve improvement = 0.70

r = reason for individuals in treatment groups = 1

d = difference you're expected to find = 0.45

n = 14 + 20% of losses = 17 patients per group

SELECTION CRITERIA TO PARTICIPATE

- Women and men aged 18 to 65 overweight or obese (BMI 25 kg/m²)
- Patients with prediabetes, defined by:
 - 1) Glucose intolerance (ITG = glucose at 2h en la CTOG between 140-199mg/dL).

2) The coexistence of fasting impaired glucose (GAA = fasting glucose between 100 and 125mg/dl) and glucose intolerance (ITG = glucose at 2h in CTOG between 140-199mg/dL).

- Those who agree to participate in the study sign an informed consent letter.

NOT SELECTED TO PARTICIPATE

- Patients with DM2 previously diagnosed or detected during sampling and CTOG.
- People currently being treated or for the past 3 months with metformin, pioglitazone, or any other antidiabetic drug, including insulin.
- Serum creatinine >1.6mg/dl.
- Very high hipertriglyceridemia (>500mg/dl).
- Pregnant women.
- Uncontrolled arterial hypertension (systólic >180mmhg o diastolic >105mmHg).
- Excessive alcohol intake, acute or chronic.

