- Medications or medical conditions affecting glucose homeostasis (thiazides, beta blockers, systemic glucocorticoids, weight-reducing or anorexigenic drugs, Cushing syndrome, thyrotoxicosis)

ELIMINATION

- Intolerance to the medicine used.
- Absence to more than 20 % of follow-up appointments.
- That they do not finalize the study and monitoring protocol.

VARIABLES

INDEPENDENT VARIABLES

- 1) *Intervention*

DEPENDENT VARIABLES

- 1) *Glucose homeostasis.*
- 2) *Sensitivity to insulin.*
- 3) *Pancreatic beta cell function.*
- 4) *Cardiovascular function.*

OPERATION OF VARIABLES, MEASUREMENT SCALES AND MEASUREMENT UNITS.

DEPENDENT VARIABLE	CONCEPTUAL DEFINITION	OPERATIONAL DEFINITION	CLASIFICATION	MEASURE- MENT LEVEL	INDICATOR
INTERVENTION	It is the established therapeutic strategy to prevent the progression of Prediabetes to type 2 diabetes mellitus and its complications.	
A. Administration of 1 tablet of linagliptin 2.5 mg /metformin 850 mg every 24 hours + 1 tablet of metformin 850 mg every 24 hours.
 
B. Administration of 1 tablet of metformin 850 mg every 12 hours.
	Qualitative	Nominal	
A. Group with low dose treatment of Linagliptin/ Metformin.
 
B. Metformin treatment group.

DEPENDENT VARIABLE	CONCEPTUAL DEFINITION	OPERATIONAL DEFINITION	CLASIFICATION	MEASUREMENT LEVEL	INDICATOR
FUNCTION OF THE PANCREATIC BETA CELL	Pancreatic beta cell's ability to secrete enough Insulin to keep blood glucose levels at normal levels.	Value obtained by the CTOG, when applying the formula $(\Delta I_{0-30})/(\Delta G_{0-30})$, (ΔI_{0-30}) = difference in insulin value measured at 0 and 30 minutes. (ΔG_{0-30}) = difference in glucose value measured at 0 and 30 minutes.	Quantitative	Reason	Pmol/mmol,
HOMEOSTASIS OF GLUCOSE	Ability of therapeutic interventions to reverse glucose intolerance.	It shall be considered as YES when the fasting glucose level at 6 months after the intervention begins, either at 2 h during CTOG is <140mg/dL, and NO when glucose levels at 2h during CTOG are 140mg/dL.	Qualitative	Dichotomous Nominal	Yes No

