SENSITIVITY TO INSULIN	Insulin's ability to promote glucose uptake by muscle tissue, and suppress glucose production by the liver and avoid the lipolysis in adipose tissue.	It will be evaluated using Matsuda's index with glucose and insulin values during CTOG using the following formula: Insulin sensitivity = $\frac{10000}{\sqrt{(G_0 \times I_0) \times (\bar{G}_{0-120} \times \bar{I}_{0-120})}}$	Quantitative	Reason	Natural numbers

CARDIO-VASCULAR FUNCTION	Function of the system made up of heart and blood vessels for transport activities.	Measurement of ejection fraction, diastolic and systolic preloads and ejection fraction.	Quantitative	Continues	Percentage %
--------------------------	---	--	--------------	-----------	--------------

METHODS.

Identification of patients at risk

During this initial phase, overweight or obese patients will be identified with and at least 2 risk factors for DM 2, who will be invited to the screening of the study and as a first step will answer a survey of nutrition and physical activity.

Recruitment of patients

Metabolic evaluation and classification of patients: Once obtaining weight and size, we identify overweight or obese patients and risk factors for DM2, they will be invited to continue the counting phase; The next step will be to cite patients for fast glucose measurement, and only patients who have a glucose level of 100mg/dL will have CTOG performed to determine the presence of prediabetes.

Glucose tolerance curve: The tolerance curve consists of citing the patient with an 8-12 hrs fast, the vein is channeled to the ulnar with 0.9% 250cc saline solution, basal blood samples are taken and 75g of glucose is given to drink and subsequently take blood samples every 30 minutes for the next two hours (0, 30, 60, 90 and 120min), for glucose determination at that time and for subsequent measurement of insulin, glucagon and GLP-1. As mentioned in the selection criteria, patients who are diagnosed with DM2 during screening (CTOG) will not be included in the study.

According to glucose values within 2 hours of oral loading, patients will be classified as:

- 1) Glucose-tolerant norms when glucose at 2hrs during CTOG is <140mg/dl,
- 2) Patients with glucose intolerance when glucose at 2hrs of CTOG is between 140 and 199mg/dL,

3) Recently diagnosed DM2 patients when glucose is 2 hrs. CTOG is 200mg/dL.

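### No baseline adjustment is planned for the numeric outcomes although baseline values are collected, and the quantity tested between groups is undefined for the cardiovascular and renal outcomes

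*Combined protocol and SAP*

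**What the plan says.** The Statistic Analysis section states: "For comparisons of numeric variables between study groups, we will use Student t if the distribution of the data follows a normality pattern". Mann-Whitney U is the fallback and chi-square is for qualitative variables. No covariate, model, effect estimate or confidence interval is named, and the section does not say whether a 6-month value or a change is tested.

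The Specific objectives fill part of the gap. For two outcomes they set an end-of-treatment comparison: "Compare insulin resistance and pancreatic beta cell function between study groups at the end of the intervention". For cardiovascular markers they say "Compare markers of cardiovascular risk before and after treatments in the 2 study groups", and for body composition "Determine changes in body composition"; neither defines a between-group quantity. The Secondary objectives ask for renal function at the beginning and end of the study, again without one. The sample-size section counts patients by improvement ("proportion of individuals in the best treatment who failed to achieve improvement = 0.25"), which can be read as relative to baseline.

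Baseline values will exist: "Once patients have all baseline measurements and have met the selection criteria, they will be randomized to one of the two interventions". The glucose tolerance test is done at screening, and echocardiography and 24-hour urine precede randomisation. The Fourth Phase repeats all three at 6 months. Randomisation is by computer-generated random numbers, with no stratification mentioned.

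**The concern.** With 14 evaluable and 17 enrolled patients per group, precision is scarce. A baseline value of the same outcome is usually the best available predictor of its 6-month value. The plan pays for these measurements and then leaves them out of the between-group comparison.

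There is also a pre-specification gap. Where the tested quantity is not fixed, the analyst can test final values or changes. The two tests can disagree, and the choice could be made after the data are seen.

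**Working it through.** **Inputs from the documents.** 14 per group evaluable, 17 enrolled, 1:1 allocation, alpha 0.05 (two-sided, from the alpha/2 in the formula). The loss step reproduces: 14 × 1.2 = 16.8, so 17. The 14 does not: the printed formula with its own inputs gives 7.9 × 0.475 × 0.525 × 2 / 0.45² = 19.5, so 20. That is a separate matter; 14 and 17 are used here as stated.

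**Inputs assumed.** The sample size rests on proportions, so no SD, mean difference or correlation is given. I take normal data with SD 1 at both visits, an effect of 1.0 SD, and rho from 0 to 0.7.

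**Variance of the estimated difference, in units of 2/n.**
- 6-month value: 1
- Change: 2(1 − rho)
- ANCOVA: (1 − rho²)k on average, with k = 1 + 1/(2n − 4) allowing for chance baseline imbalance. At n = 14, k = 25/24 = 1.042.

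**Break-even for the variance.** ANCOVA beats the 6-month value when rho > √(1 − 1/k): 0.20 at n = 14 and 0.18 at n = 17. It beats change when rho < 2/k − 1: 0.92 and 0.94.

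**Power at 1.0 SD.** Noncentral t with 2n − 2 degrees of freedom for the two unadjusted tests. For ANCOVA, 2n − 3, averaged over the baseline gap. Effective n is n / [(1 − rho²)k].

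| n per group | rho | 6-month t | change t | ANCOVA | effective n |
|---|---|---|---|---|---|
| 14 | 0 | 72.1% | 43.7% | 70.3% | 13.4 |
| 14 | 0.3 | 72.1% | 57.7% | 74.3% | 14.8 |
| 14 | 0.5 | 72.1% | 72.1% | 82.1% | 17.9 |
| 14 | 0.7 | 72.1% | 90.8% | 93.6% | 26.4 |
| 17 | 0 | 80.7% | 51.6% | 79.4% | 16.5 |
| 17 | 0.3 | 80.7% | 66.6% | 83.0% | 18.1 |
| 17 | 0.5 | 80.7% | 80.7% | 89.4% | 21.9 |
| 17 | 0.7 | 80.7% | 95.4% | 97.3% | 32.3 |

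**Skewed data.** Log-normal, log SD 0.5, effect 1.0 SD on the log scale, 14 per group, 40,000 simulations: Mann-Whitney on 6-month values has about 70% power. ANCOVA on logs has 71%, 74%, 82% and 94% at rho 0, 0.3, 0.5 and 0.7. The pattern is the same.

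**Open choice of quantity.** Under no effect, I simulated both t-tests and counted a trial as positive if either was significant (200,000 trials per cell). At rho 0.3, 0.5 and 0.7 this gave 8.8% to 9.5% at both sample sizes. Two independent 5% tests would give 1 − 0.95² = 9.75%, so about 9% is close to the ceiling.

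**Chance imbalance.** At 14 per group, a baseline gap above 0.5 SD on a given outcome occurs in 18.6% of trials. At rho 0.5 the 6-month t-test then rejects a true null 11.1% of the time, against 3.6% otherwise. Overall: 0.186 × 0.111 + 0.814 × 0.036 = 0.050. ANCOVA stays near 5% in both sets of trials.

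**The case against.** The strongest reply is that nothing here is invalid. Over all randomisations both planned tests hold 5%. A reader might infer from the imbalance figures that the plan is biased or inflates error; the 5.0% overall rate shows that it does not.

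A reader might also infer that the plan never says what is tested. That is too strong. For insulin resistance and beta-cell function the objectives point to end-of-intervention values. The body-composition and cardiovascular lines concern other outcomes and may describe within-group aims, so no single outcome is given two conflicting between-group quantities. The gap is confined to the other outcomes, chiefly cardiovascular and renal.

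Nor does the plan produce a 9% error rate. That needs both tests to be run and any significant one reported.

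Finally, the gain is not fixed by the documents. At 14 per group and 1.0 SD it runs from −2 to +21 points, depending only on rho, and at rho 0.3 it is just 2. A larger effect leaves less to gain at low rho. If 75% versus 30% is converted to a latent normal scale, the effect is 0.674 + 0.524 = 1.2 SD. The 6-month t-test then already has 86% power at 14 per group, and ANCOVA adds about 2 points at rho 0.3. That conversion is only illustrative: if improvement means change from baseline, the 1.2 is in SDs of change.

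All of this stands. It limits the point to efficiency and pre-specification; it does not remove it. No outcome has a planned baseline adjustment.

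**Conclusion.** The point holds as a loss of efficiency in a valid analysis, with a gap in pre-specification for the cardiovascular and renal outcomes. The missing covariate is certain from the text. The size of the gain is not: it rests on an assumed rho, an assumed 1.0 SD effect, normality and equal SDs. On those assumptions, at 14 per group, ANCOVA has 70% to 94% power over rho 0 to 0.7, against 72% for a 6-month t-test. The possible loss is about 2 points and the possible gain about 21. At rho 0.5, 14 per group are worth about 18. The false-positive rate of about 9% is a worst case, and it does not apply to insulin resistance or beta-cell function if the objectives are followed. The change should be made, but the trial is not unsound without it.

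**What to change.** In the Statistic Analysis section:

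- For each numeric outcome measured the same way at both visits, make ANCOVA of the 6-month value, on treatment and that outcome's own baseline value, the main between-group analysis. This also settles the tested quantity for the cardiovascular and renal outcomes.
- Report the adjusted difference with its ordinary 95% confidence interval, or an adjusted ratio where logs are used (for example, the Matsuda index). Fix the scale for each outcome before unblinding.
- The 0–30 minute insulin/glucose ratio can be zero or negative, so logs are unsafe. Use ANCOVA on the original scale with its ordinary interval, and a rank-based ANCOVA as sensitivity analysis. In a skewed simulated example at these sample sizes the ordinary interval covered 94.7% to 95.7%, whereas a percentile bootstrap covered only 92% to 93%, so a bootstrap is not advised.
- Keep Student t and Mann-Whitney on 6-month values as sensitivity analyses.

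Body composition falls outside this rule as written: it is measured by DEXA at baseline and apparently by impedance at 6 months.

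The cost is SAP wording and a decision on scale for each outcome. No visit, sample or patient is added. Statistically, it takes one degree of freedom per outcome and about 2 points of power if rho is 0 (14 per group, 1.0 SD).

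### The plan names no primary outcome, deciding analysis set, testing order or success rule, so either the stated alpha of 0.05 or the stated 80% power does not hold for its main outcomes

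*Combined protocol and SAP*

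**What the plan says.** - **Hypothesis.** The combination "has a greater effect on pancreatic beta cell function, insulin resistance and cardiovascular function compared to metformin alone". The three outcomes are joined by a conjunction and none is ranked.
- **Specific objectives.** Only one objective compares the arms on these outcomes at the end of treatment, and it covers two of them: "Compare insulin resistance and pancreatic beta cell function between study groups at the end of the intervention". Cardiovascular risk markers have their own before-and-after objective.
- **Secondary objectives.** This heading sets apart adherence, diabetes incidence and renal function. It does not order the main outcomes.
- **Sample size.** The combination is expected to "improve the outcome variables (insulin resistance, pancreatic beta cell function and cardiovascular function) by at least 75" per cent, "with a type I (alpha) error of 0.05 and a sample power of 80" per cent. The calculation compares two proportions and ends with "n = 14 + 20% of losses = 17 patients per group".
- **Variables.** Four dependent variables are listed without ranking: the three above and a yes/no glucose homeostasis endpoint. Cardiovascular function covers more than one echocardiographic measure.
- **Elimination.** Patients are removed for drug intolerance, for not finishing, or for "Absence to more than 20 % of follow-up appointments". The set they leave is not stated.
- **Statistic analysis.** Numeric variables are compared by Student t or Mann-Whitney, qualitative ones by chi-square. On sets and significance the section says only "Analysis by intent to be treated and analyzed by protocol shall be performed and considered as significant when the p-value is <0.05".

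**The concern.** An alpha of 0.05 describes one test, or a family of tests with a stated rule. Here several tests carry that alpha, and the plan does not say how their results combine into a conclusion. Two rules are open.

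- **Any one suffices.** One significant outcome could be presented as support at the 5% level when the chance of at least one false positive is two to three times that.
- **All are required.** The error is controlled, but the trial is more likely to miss a real effect than the stated power suggests.

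Running two analysis sets under the same threshold adds a second choice. All of these choices could be made after the results are seen, and the headline conclusion depends on them.

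**Working it through.** **Inputs from the documents:** alpha 0.05; power 80%; failure proportions 0.25 and 0.70; difference 0.45; allocation 1:1; 14 per group, raised to 17; three main outcomes; two analysis sets. The printed constant 7.9 is close to (1.96 + 0.84)² = 7.84, so the tests are two-sided.

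**Assumptions, not in the documents:** equal correlations of 0 to 0.8 between outcomes; normal data; 17 measured patients per arm; one to three per arm excluded from the per-protocol set for reasons unrelated to outcome.

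**1. The plan's own figures.** With mean proportion (0.25 + 0.70)/2 = 0.475, the printed formula gives 7.9 × 0.475 × 0.525 × 2 / 0.45² = 19.46, not 14. That mismatch is a separate matter and nothing below rests on it. The exact power of an uncorrected chi-square test for 0.25 against 0.70 is 79.9% at 17 per arm and 66% at 14. So 80% per test is a fair, slightly generous, starting point if nobody is lost.

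**2. Any one outcome counts, one set.** If the outcomes are independent:
- three outcomes: 1 − 0.95³ = 14.3%
- two outcomes: 1 − 0.95² = 9.8%

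Correlation lowers these. Simulated t tests at 17 per arm (200,000 runs) give, for three outcomes, 14.3%, 13.7%, 12.6% and 9.9% at correlations 0, 0.3, 0.5 and 0.8. For two outcomes they give 9.8%, 9.5%, 9.1% and 7.9%.

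**3. Two sets.** For a single outcome, P(significant in either set) = 0.05 + 0.05 − P(significant in both). The result therefore depends on how far the sets differ. For any of three outcomes:

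| Rule | Excluded per arm | Correlation 0 | Correlation 0.8 |
|---|---|---|---|
| One set only | – | 14% | 10% |
| Same outcome significant in both sets | 1 | 11% | 8% |
| Same outcome significant in both sets | 3 | 9% | 6% |
| Significant in either set | 1 | 17% | 12% |
| Significant in either set | 3 | 20% | 14% |

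Every row is above 5%.

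**4. All three required.** A false claim needs at least one true null to be rejected at 0.05, so the error cannot exceed 5%. With 80% power per test and independent outcomes, joint power is 0.8³ = 51%. At a common correlation of 0.8 the simulated value is 68%. If the two glucose-curve indices correlate at −0.5 and echocardiography is independent, it is 49%. The simulated values set each test to 80% through an assumed standardised difference of 0.99 at 17 per arm. They illustrate the loss and do not predict this trial.

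**5. Fixed order.** Each test is made at 0.05 and only if the one before is significant, so the first true null reached is rejected with probability 0.05. The error over the whole sequence is at most 5%.

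**The case against.** **The conjunction.** The strongest reply is that the hypothesis joins the three outcomes with a conjunction, in its null form as well. Read literally, all three are needed and no error is inflated. A reader might otherwise infer that the trial has a 10-14% false-positive rate. The documents do not support that, because they never say that one outcome suffices. But the analysis section does not turn the conjunction into a decision rule either, and if it did, the 80% power would not be the power of that rule.

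**The family.** The between-group objective names only two outcomes, which gives 8-10%. That stands as a narrower reading. The hypothesis and the sample size still name three.

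**Direction.** If only results favouring the combination count, the figures for three outcomes are 7.4% to 5.0%, against 2.5% for one test. The baseline halves as well, so the ratio is about the same.

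**The two sets.** The plan's wording could mean that significance is needed in both. That is as open as accepting either, and gives 6-11%. Nor should 20% be read as a ceiling. It assumes exclusions unrelated to outcome, whereas intolerance and absence need not be random or equal by arm.

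**No defined test at all.** A reader might say that alpha and power refer to nothing. That is too strong. The sample size specifies a two-proportion comparison and the analysis names chi-square for qualitative variables. What is missing is which endpoint is compared and, for the three named outcomes, who counts as improved.

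**Elimination.** Applying these criteria to the per-protocol set alone is the natural reading, since both sets are planned. The text does not say so, and with 17 per arm it should.

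**Conclusion.** The concern holds in conditional form. No primary outcome, deciding set, testing order or success rule is stated, and each open reading breaks one of the two stated design figures.

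- **Any one of three, one set:** about 10-14% two-sided error against 5%; 8-10% for the two outcomes in the between-group objective.
- **Same outcome in both sets:** about 6-11%. **Either set:** about 12-20%.
- **All three required:** error at or below 5%, but joint power about 50-68% when each test has 80%.

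The error ranges rest on assumed correlations of 0 to 0.8; at 0.9 the any-of-three figure falls to about 8%, still above 5%. The two-set ranges also assume one to three outcome-unrelated exclusions per arm. That the rules are absent rests on the text alone. The documents do not show which reading the sponsor intends, so no single error rate can be assigned to the trial.

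**What to change.** Before unblinding, add to the Statistic analysis section:

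- One primary between-group comparison at 6 months, chosen by the sponsor, in all randomised patients by assigned group, at two-sided 0.05. If cardiovascular function is chosen, name one echocardiographic measure.
- The remaining main outcomes in a stated fixed order, each at 0.05 and only if the one before is significant. Say whether glucose homeostasis is among them.
- The Elimination criteria define the per-protocol set only.
- The per-protocol set and all other variables are supportive, reported as estimates with 95% confidence intervals.
- Alpha 0.05 refers to this sequence. The 80% power is not attached to the primary test unless it is recalculated for that test.

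This costs a few sentences and no extra patients or visits. The downside is that a later outcome cannot be claimed as confirmed if an earlier one fails, so the order matters. The documents do not give the trial's status. If the allocation has already been revealed, the choice can no longer be presented as pre-specified.
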